5.2.3 Duration of Follow-up

Participants will be followed for 18 months after removal from protocol therapy or until death, whichever occurs first. Participants removed from protocol therapy for unacceptable adverse event(s) will be followed until resolution or stabilization of the adverse event.

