7.16 Other procedures and variables

7.17 Appropriateness of procedures / measurements

The assessments described in the previous sections are widely used and generally recognized as reliable, accurate, and relevant for determining the safety and efficacy of therapies in this disease.

8. Statistical methods and determination of sample size

Primary Aim

“The values in this protocol have been revised as per the United States (US) National Institute of Standards and Technology (NIST) standardization update (agreed on 17 MAR 2015)”

Bone scan response is defined as a $\geq 30\%$ decrease in quantitative bone scan lesion area (BSA) from baseline to the end of month 2 of Ra-223 treatment (i.e. after 2 of 6 possible Ra-223 doses). In a one-stage design, 22 subjects will be enrolled to evaluate the primary endpoint of bone scan response. Assuming 90% of subjects with adequate data, the evaluable sample size is 20 subjects. With 20 subjects, given target power of 90% and 1-sided 5% alpha, a null hypothesis of $\leq 10\%$ versus an alternative hypothesis of $\geq 35\%$ in the proportion of patients achieving response can be evaluated. If 5 or more responses are observed in 20 subjects, this method of response assessment will be considered promising.

Operating characteristics

Probability of ≥ 5 responses in 20 pts	True but unknown rate of Bone Scan Response Rate					
	10%	15%	20%	25%	30%	35%
Probability of ≥ 5 responses in 20 pts	0.04	0.17	0.37	0.59	0.76	0.88

Secondary Aims

A key secondary objective is to evaluate whether quantitative analysis of ^{99m}Tc -MDP bone scan after 2 months of therapy can identify patients who will achieve long term clinical benefit. Towards this end, all subjects will be treated and followed for at least 18 months. Survival status at 18 months will be ascertained (i.e. dichotomized as survivor or non-survivor at 18 months). A two-sample t-test will be used to determine the difference in mean percent change in BSA between survivor and non-survivor groups. Reported median survival for the study cohort of the ALSYMPCA trial was 14.9 months. Assuming events follow an exponential distribution this parallels an 18-month survival rate of 43%. The detectable difference will depend on the variability in change in BSA as measured by standard deviation (SD). There is 80% power to detect an effect of 1.332 SD given a 2-sided 0.05 alpha and 20 evaluable patients divided as 9 survivors and 11 non-survivors.

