Bone scans are scheduled for the beginning of month 3/end of month 2 (T3), and one month post month 6 (FU1M). Descriptive statistics on absolute and percent change in BSA from baseline to these study timepoints will be provided for the overall study cohort and within survivor groups. By the end of month 2, bone scan response is expected in 35% of subjects. Patients will be cross-classified by bone scan response status at 2 months and survival status at 18 months. Agreement will be quantified using Cohen's Kappa; however, the sample size is too small to produce a realistic confidence interval. Kappa is assessed as follows: <0.00, poor; 0.00-0.20, slight; 0.21-0.40, fair; 0.41-0.60, moderate; 0.61-0.80, substantial; 0.81-1.00, almost perfect; and 1.00, perfect. Survival time defined as the time from registration to death, or if censored to date last known alive will be calculated. Correlation between change in BSA after 2 months and survival time will be assessed graphically with scatter plots and using Pearson correlation coefficient. Survival distributions will also be estimated using the Kaplan-Meier method in a landmark analysis at 2 months. Survival time is defined as the time from response classification (at 2 months) to death, or if censored to date last known alive. Cox proportional hazards (PH) regression will be used to estimate the bone scan response hazard ratio along with 95% confidence limits.

This study also affords insights into several other potential biomarkers including measures related to circulating tumor cells (number, proliferative index, AR signaling, markers of DNA damage/repair), bone turnover (BAP, NTx), inflammation and angiogenesis. Fluciclovine PET imaging will occur in 10 subjects at baseline and the end of month 2 of treatment. All other measures will occur at baseline, during treatment, and post treatment as detailed in the required data table. Descriptive statistics will be provided for each measure and timepoint along with absolute and percentage change from baseline. Association with overall survival and response will be analyzed as exploratory similar to the methods above for bone scan.

Accrual Targets

Accrual Targets						
Ethnic Category	Sex/Gender					
	Females		Males		Total	
Hispanic or Latino	0	+	1	=	1	
Not Hispanic or Latino	0	+	21	=	21	
Ethnic Category: Total of all subjects	0	(A1)	+	22	(B1) = 22 (C1)	
Racial Category						
American Indian or Alaskan Native	0	+	0	=	0	
Asian	0	+	1	=	1	

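### No planned analysis relates continuous month-2 BSA change to survival time with a method that handles censoring, although one change to the planned landmark Cox model would do it

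*Combined protocol and SAP*

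**What the plan says.** Under Secondary Aims, Section 8 of the combined protocol and SAP sets out four analyses of BSA change against survival.

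- **t-test.** Survival is first cut in two: "Survival status at 18 months will be ascertained (i.e. dichotomized as survivor or non-survivor at 18 months". Then: "A two-sample t-test will be used to determine the difference in mean percent change in BSA between survivor and non-survivor groups". This is the only secondary analysis with a power statement: "There is 80% power to detect an effect of 1.332 SD". The calculation takes 9 men alive and 11 dead out of 20, tested two-sided at the 5% level.
- **Kappa.** Response at 2 months is cross-classified with survival status at 18 months, so both variables are binary.
- **Pearson correlation and scatter plot.** Change in BSA after 2 months is correlated with survival time. Survival time runs from registration to death or, for a censored man, to the date he was last known alive.
- **Landmark analysis at 2 months.** Kaplan-Meier curves are followed by a Cox model: "Cox proportional hazards (PH) regression will be used to estimate the bone scan response hazard ratio along with 95% confidence limits".

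The documents give more than one follow-up length. Section 5.2.3 states: "Participants will be followed for 18 months after removal from protocol therapy or until death, whichever occurs first". The key to the Section 7.1.1 table likewise counts the 18-month visit from the final Ra-223 treatment. The Timeline in Section 8 gives 18 months per subject for treatment and follow-up together, with all follow-up complete 30 months after activation.

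**The concern.** Each planned analysis gives up something different. The t-test scores a death at month 3 and a death at month 17 alike, and does not use deaths after month 18. The Cox model handles censoring but treats a 31% and an 80% fall in BSA alike, and separates a 29% fall from a 31% fall. The Pearson coefficient keeps both scales, but a man alive at month 18 and a man who dies at month 18 enter with the same value. With 43% expected alive at 18 months, that affects a large share of the sample, and the coefficient then depends on how long survivors happened to be followed.

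With 20 evaluable men and about 11 deaths by month 18, little information can be spared. Section 8 also says that the other biomarkers will be related to overall survival by similar methods, so the gap carries over to them. A smaller point is that the plan does not say how a man lost before month 18 is classified for the t-test. A Cox model would use his follow-up.

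**Working it through.** **1. The plan's own figures.** All inputs are from Section 8: median survival 14.9 months, exponential survival, 20 evaluable men, two-sided alpha 0.05.

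- Survival at 18 months = exp(-ln 2 × 18/14.9) = 0.433. Then 20 × 0.433 = 8.7, so 9 survivors and 11 non-survivors.
- Noncentrality = 1.332 × √(9 × 11/20) = 1.332 × 2.225 = 2.964. With 18 degrees of freedom, noncentral-t power is 0.8002.

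Both stated figures (43%, and 80% power at 1.332 SD) reproduce.

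**2. What each analysis keeps.**

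| Analysis | BSA change continuous | Survival time kept | Censoring handled |
|---|---|---|---|
| t-test | yes | no | not applicable |
| Kappa | no | no | not applicable |
| Pearson | yes | yes | no |
| Landmark Cox on response | no | yes | yes |

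No row has yes in all three columns.

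**3. Size of the loss under a graded effect.** The documents state no model linking BSA change to time of death, so one is assumed. BSA change is standard normal, survival is exponential, the log-hazard is linear in BSA change with slope b per SD, and 18-month survival is held at 43.3%. There are 20 men and 40,000 simulated trials per row. Follow-up is 18 months, or 23 months as an approximation to Section 5.2.3: the sixth dose falls at 5 × 28 = 140 days, or 4.6 months, and 4.6 + 18 = 22.6. The critical value of the continuous Cox likelihood-ratio test is recalibrated to 5% size. The yes/no Cox uses 35% responders, as Section 8 expects, and its nominal score test.

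| b | Survivor gap (SD) | t-test | Continuous Cox, 18 mo | Continuous Cox, 23 mo | Yes/no Cox, 18 / 23 mo |
|---|---|---|---|---|---|
| 0.5 | 0.71 | 0.30 | 0.33 | 0.36 | 0.18 / 0.21 |
| 0.7 | 0.95 | 0.49 | 0.55 | 0.59 | 0.30 / 0.34 |
| 0.9 | 1.17 | 0.66 | 0.75 | 0.78 | 0.42 / 0.47 |
| 1.08 | 1.33 | 0.78 | 0.86 | 0.89 | 0.52 / 0.57 |

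The t-test shows 0.78 rather than 0.80 at the plan's gap because the split between survivors and non-survivors varies from trial to trial. A slope of 1.08 is a hazard ratio of exp(1.08) = 2.9 per SD, a very large effect.

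**4. The landmark version.** With survival counted from month 2, as the planned Cox model does, power at the 1.332 SD gap is 0.79 for the t-test and, for continuous Cox, 0.84 to month 18 or 0.88 to month 22.6. The gain is 5 to 9 points.

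**5. Pearson in the same model.** Size-adjusted power is about 0.82-0.86 at the same gap. Its weakness is the treatment of censoring more than power.

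**6. The opposite case.** Fix 9 survivors and 11 non-survivors, shift BSA change by 1.332 SD between them, and let it have no relation to time of death within either group. The t-test then has 0.80 power. Continuous Cox has 0.74 at 18 months, 0.67 at 23 and 0.66 at 24.

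**7. Size of the Cox test.** Under the null, the nominal 5% likelihood-ratio test rejects in 5.7% of trials at 18 months and 5.8-5.9% at 23-24 months.

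**The case against.** The strongest defence is that the t-test answers the question the protocol asks. The synopsis and Section 2 want mean percent change described by 18-month survival status, and long-term benefit is naturally read as being alive at a fixed time. A hazard ratio per SD answers a related but different question. This stands, and it is the reason to keep the t-test.

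A reader might infer that the powered test simply throws away 8 to 11 points of power and should be replaced. The documents do not support that. The range depends on an assumed graded hazard and on very large effects, and its upper part needs follow-up beyond 18 months, on which the documents disagree. In the opposite case above, full-follow-up Cox loses about 12-14 points to the t-test. Nothing in the documents favours one scenario over the other.

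Nor does the plan ignore survival time or later deaths, since the Pearson, Kaplan-Meier and Cox analyses all use them. Pearson comes within about 3 points of continuous Cox in the graded model. What remains against it is narrower: it has no means of handling censored times, so its value shifts with the length of follow-up.

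Finally, this is a secondary analysis in a 22-man exploratory study. The only decision rule is 5 or more responses in 20, and it is unaffected.

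**Conclusion.** The point holds as a gap in the set of analyses. There is no error in the t-test or its power statement. No analysis in Section 8 combines continuous BSA change with survival time under a method that handles censoring.

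Under a log-linear hazard and the plan's 1.332 SD gap, the missing model has about 84-88% power, against about 78-79% for the t-test and about 50-60% for the planned yes/no Cox. The gain over the t-test is about 4-8 points at 0.8 SD, where every test is weak. If BSA change is unrelated to time of death within the survivor groups, the t-test is better, at about 78-80% against 64-73%.

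The case for the change therefore rests on a clear improvement over the yes/no Cox and on proper treatment of censoring compared with Pearson. It does not rest on a guaranteed gain over the t-test. The change is a worthwhile, low-cost refinement, and no conclusion of the trial depends on it.

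**What to change.** In Section 8, Secondary Aims:

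- Fit the planned 2-month landmark Cox model with percent change in BSA as a continuous covariate. Report the hazard ratio per SD or per 10-point change, chosen in advance, with its 95% CI and a likelihood-ratio or permutation p-value.
- Make this the main analysis of BSA change against survival time, in place of the Pearson coefficient. Keep the scatter plot and the response hazard ratio as descriptions.
- Keep the 18-month t-test and its 80% power statement for the stated objective.
- Reconcile the follow-up length in Sections 5.2.3 and 7.1.1 with the Timeline in Section 8 before quoting any power beyond 18 months. If power is quoted for the new model, compute it for the landmark version and state the assumed hazard model.

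The cost is a few lines of SAP text and one model, with no extra men, scans or visits. The model assumes proportional hazards and a linear effect of BSA change, neither of which 20 men can test well. Its asymptotic test is slightly liberal at this sample size, so the permutation p-value is the safer choice.

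### The response-by-survival table is summarised only by a graded kappa, which merges predictive value with sensitivity; report classification measures with exact intervals instead

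*Combined protocol and SAP*

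**What the plan says.** Section 8, Secondary Aims, sets a key secondary objective: whether the quantitative bone scan after two months of treatment "can identify patients who will achieve long term clinical benefit". Survival at 18 months is dichotomised, and the table is then described: "Patients will be cross-classified by bone scan response status at 2 months and survival status at 18 months". Agreement in that table is to be measured with Cohen's kappa. The plan adds that the sample is too small for a realistic confidence interval, and gives a verbal scale whose upper end reads "0.61-0.80, substantial; 0.81-1.00, almost perfect; and 1.00, perfect".

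The same section supplies the expected margins. For response: "By the end of month 2, bone scan response is expected in 35% of subjects". For survival, the power statement for the t-test is "given a 2-sided 0.05 alpha and 20 evaluable patients divided as 9 survivors and 11 non-survivors".

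Section 8 names no sensitivity, specificity, positive predictive value (PPV) or negative predictive value (NPV). It also does not say that unequal margins limit kappa. Kappa is not the only analysis of this aim. The plan also has a t-test of percent change in lesion area by survival group, a Pearson correlation with survival time, and a landmark Kaplan-Meier and Cox analysis from month 2.

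**The concern.** Kappa was built for two ratings of the same thing and treats them symmetrically. Here one variable is an imaging change at 2 months and the other is vital status at 18 months, and the plan expects them at different rates. The aim has a direction: given the scan, who will be alive? A reader wants two separate answers: how often a responder survives, and how many of the survivors the scan finds. Kappa mixes both into one number that also moves with the margins.

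At stake is how a key secondary result is reported. A label such as *moderate* could describe a marker whose responders all survive, or one whose responders often die. Because no interval is planned for kappa, the label would also appear with no statement of its uncertainty. Section 8 says the other biomarkers will be analysed in a similar way, so the choice may carry over to them.

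**Working it through.** **Inputs, all from Section 8.** Evaluable patients: "Assuming 90% of subjects with adequate data, the evaluable sample size is 20 subjects". Expected response 35%, so 0.35 × 20 = 7 responders. Survival: "Reported median survival for the study cohort of the ALSYMPCA trial was 14.9 months". I assume that 18-month status is known for all 20.

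**The plan's own figures reproduce.** Under exponential survival, S(18) = exp(−ln 2 × 18/14.9) = 0.433, the stated 43%. Then 20 × 0.433 = 8.66, rounded in the plan to 9 survivors and 11 non-survivors. A two-sample t-test with 9 and 11 patients, two-sided alpha 0.05 and a difference of 1.332 SD has power 0.800, as stated. The plan gives no expected or maximum kappa to reproduce.

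**Formula.** Let the cells be (responder alive, responder dead, non-responder alive, non-responder dead) = (a, b, c, d). Then po = (a + d)/n, pe = [(a + b)(a + c) + (c + d)(b + d)]/n², and kappa = (po − pe)/(1 − pe). For fixed margins, kappa is largest when the smaller of the responder and survivor totals all falls in cell a.

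**Maximum at the planned counts (7 responders, 9 survivors).** Table (7, 0, 2, 11): po = 18/20 = 0.90; pe = (7×9 + 13×11)/400 = 206/400 = 0.515; kappa = 0.385/0.485 = 0.794.

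**Maximum at the plan's rates before rounding (35% and 43%).** po = 1 − 0.08 = 0.92; pe = 0.35×0.43 + 0.65×0.57 = 0.521; kappa = 0.399/0.479 = 0.833.

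**Maximum at neighbouring counts.** 7 responders and 8 survivors: 0.894. 8 responders and 9 survivors: 0.898. Equal margins: 1.00.

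**Nine survivors, every responder alive, number of responders varied:**

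| Responders | Table | po | pe | Kappa | Plan's label | PPV | Sensitivity | NPV |
|---|---|---|---|---|---|---|---|---|
| 7 | (7, 0, 2, 11) | 0.90 | 0.515 | 0.794 | substantial | 7/7 = 100% | 7/9 = 78% | 11/13 = 85% |
| 5 | (5, 0, 4, 11) | 0.80 | 0.525 | 0.579 | moderate | 5/5 = 100% | 5/9 = 56% | 11/15 = 73% |
| 3 | (3, 0, 6, 11) | 0.70 | 0.535 | 0.355 | fair | 3/3 = 100% | 3/9 = 33% | 11/17 = 65% |

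Five responders is the plan's own threshold for calling the method promising.

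**Same label, different marker.** Table (7, 2, 2, 9): po = 0.80, pe = 202/400 = 0.505, kappa = 0.295/0.495 = 0.596, with PPV and sensitivity both 7/9 = 78%. This is *moderate*, as is (5, 0, 4, 11), which has PPV 100% and sensitivity 56%. Likewise (6, 3, 3, 8) gives 0.195/0.495 = 0.394 with PPV 6/9 = 67%. It shares the label *fair* with (3, 0, 6, 11), where PPV is 100%.

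**Exact (Clopper-Pearson) 95% intervals for (7, 0, 2, 11).** PPV 7/7: 59–100%. NPV 11/13: 55–98%. Sensitivity 7/9: 40–97%. Specificity 11/11: 72–100%.

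**The case against.** The strongest reply is that kappa falls across the three tables for a good reason. With 7, 5 and 3 responders the scan misses 2, 4 and 6 of the 9 survivors, and NPV falls as well. If the aim is to find the men who will do well, a scan that misses 6 of 9 does so poorly, and *fair* is defensible. This stands: the falling grade partly reflects a real loss of sensitivity and is not a pure artefact of the response rate. What remains is that the label cannot show which property was lost, as the pairs of tables with a shared label demonstrate.

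Second, other planned analyses bear on the same aim. That is also true. But the t-test compares mean changes, Pearson uses the continuous change, and Cox gives a hazard ratio. The landmark Kaplan-Meier curves could yield survival by response group, but Section 8 names no 18-month estimate by group, and they give no sensitivity or specificity. The two-by-two table is the only planned analysis that classifies each patient.

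Third, no decision rests on kappa, the study is exploratory, and the plan admits the small-sample limit. This bears on importance, and it is why the point is only a cheap improvement.

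Fourth, exact intervals suffer from the same small sample: PPV is 48–100% for 5/5 and 29–100% for 3/3. Agreed. They make the imprecision visible, which a bare label does not.

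**Conclusion.** The point holds as a mismatch between a predictive aim and the single summary chosen for its classification table. Its size is shown by the movement from 0.79 to 0.58 to 0.36, three different labels, while PPV stays at 100% and sensitivity drops from 78% to 33%. Those figures assume 20 patients with known status, 9 survivors and no deaths among responders.

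Three stronger readings are tempting, and the documents do not support them.

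- A reader might infer that *almost perfect* can never be reached. That is so at exactly 7 responders and 9 survivors, where the maximum is 0.79. The count of 9 comes from rounding 8.66 up; at the stated 35% and 43% the maximum is 0.83, and one fewer survivor or one more responder lifts it to about 0.89–0.90. The margins are also observed, not fixed. If every responder survives and response is 35%, the chance that kappa is at least 0.81 (to two decimals) is about 0.51 at 43% survival and 0.39 at 45%.
- A reader might infer that perfect prediction is capped at 0.79. The table giving 0.79 is not perfect prediction, because two survivors are non-responders. Perfect prediction needs equal margins and gives 1.00.
- A reader might infer that the aim cannot be answered as planned. Kappa is one descriptive measure among several; it just does not answer the question directly.

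The primary endpoint and the rule of 5 or more responses in 20 are untouched.

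**What to change.** In Section 8, Secondary Aims, make sensitivity, specificity, PPV and NPV of month-2 response for 18-month survival the summary of the two-by-two table, each with an exact 95% interval. If kappa is kept, report it as descriptive, without the verbal grades and beside its maximum at the observed margins.

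The cost is a change of wording. The same table supplies every figure, with no new patients, visits or data. The drawback is that the intervals will be wide at 20 patients, for example 40–97% for a sensitivity of 7/9, and the report should present them as such.

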(7) Analgesic use and other patient reported outcomes will be collected as detailed in Appendices D, E, and F.

Abbreviations:

S, screening; B, baseline;

T1 D1, Ra-223 treatment 1 day 1;

F/U 1M, follow-up visit 1 month after final Ra-223 treatment;

F/U 4M, follow-up visit 4 months after final Ra-223 treatment;

F/U 18M, follow-up visit 18 months after final Ra-223 treatment;

CT a/p, CT of the, abdomen, and pelvis;

Chemistry panel, includes liver panel also known as LFTs; CBC, complete blood count;

PSA, serum prostate specific antigen;

PET, positron emission tomography;

CTCs, circulating tumor cells;

BAP, bone-specific alkaline phosphatase; NTx, n-telopeptide.

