Black or African American	0	+	1	=	1	
Native Hawaiian or other Pacific Islander	0	+	0	=	0	
White	0	+	20	=	20	
Racial Category: Total of all subjects	0	(A2)	+	22	(B2) = 22 (C2)	
	(A1 = A2)		(B1 = B2)		(C1 = C2)	

Timeline

We anticipate an average of 2 subjects to be accrued monthly (approximate accrual time: 12 months). The primary endpoint (assessment of change in total area of bone metastases by ^{99m}Tc MDP bone scan) is assessed 2 months after the start of treatment; the primary analysis will take place 14 months after study activation. With an anticipated 12 month enrollment period and per-subject 18 months of study-directed treatment and follow-up, the last enrolled patient will conclude follow-up 30 months after activation.

Notable anticipated dates and analyses are as follows:

- T: 0m Study opens for accrual at MGH
- T: 12m Study accrual completed
- T: 14m Primary analysis
- T: 30m Completion of all study follow-up

9. Data handling and quality assurance

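### The Pearson correlation of month-2 BSA change with survival time treats censored follow-up as time to death, and no planned time-to-event model uses continuous BSA change

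*Combined protocol and SAP*

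**What the plan says.** All of this is in Section 8, Secondary Aims, unless stated otherwise.

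- The time variable: "Survival time defined as the time from registration to death, or if censored to date last known alive will be calculated".
- The next sentence: "Correlation between change in BSA after 2 months and survival time will be assessed graphically with scatter plots and using Pearson correlation coefficient". It neither restricts the calculation to deaths nor adjusts for censoring.
- The survival regression: "Cox proportional hazards (PH) regression will be used to estimate the bone scan response hazard ratio along with 95% confidence limits". Its covariate is the binary response of at least a 30% decrease, with time counted from the 2-month landmark.
- The other inferential use of continuous change: "A two-sample t-test will be used to determine the difference in mean percent change in BSA between survivor and non-survivor groups". Survivor status is taken at 18 months.
- Length of follow-up: Secondary Aims says "all subjects will be treated and followed for at least 18 months". The Timeline gives "per-subject 18 months of study-directed treatment and follow-up, the last enrolled patient will conclude follow-up 30 months after activation". Section 5.2.3 says "Participants will be followed for 18 months after removal from protocol therapy or until death, whichever occurs first", and the Section 7.1.1 abbreviations agree with it: "F/U 18M, follow-up visit 18 months after final Ra-223 treatment".
- The circulating tumour cell, bone turnover, inflammation and angiogenesis markers are to be related to survival by similar exploratory methods.

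**The concern.** For a man alive at last contact, only a lower bound on survival is known. Putting that bound into a Pearson coefficient treats it as the survival time. The resulting r then depends on how long patients were followed as well as on how BSA change relates to survival. If follow-up differs between patients, r no longer estimates a clearly defined quantity.

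The plan calls it a key secondary objective to learn whether the month-2 scan identifies men with long-term benefit. Pearson r is its only measure linking the full scale of BSA change to the full scale of survival time. The same approach is carried over to the other biomarkers.

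**Working it through.** **Inputs.** From Section 8: median survival 14.9 months, exponential; 20 evaluable patients split 9/11; detectable effect 1.332 SD at 80% power, two-sided 0.05. From Section 7.1.1: doses every 4 weeks, so the sixth falls 140 days after the first. Hazard ratios, distribution shapes and loss rates are not in the documents and are assumed below.

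**1. The plan's own figures.** S(18) = exp(-ln 2 × 18/14.9) = exp(-0.837) = 0.433, the stated 43%. 20 × 0.433 = 8.7, which gives the 9/11 split. Exact noncentral-t power at 1.332 SD with 9 and 11 patients is 0.800. All reproduce.

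**2. Share of values that are follow-up lengths.**
- Follow-up stops at 18 months (Timeline): 43.3%, about 9 of 20, leaving 20 × 0.567 = 11.3 deaths.
- 18 months after a sixth dose (Sections 5.2.3 and 7.1.1): 18 months + 140 days = 22.6 months; exp(-ln 2 × 22.6/14.9) = 0.349, about 7 of 20, leaving 20 × 0.651 = 13.0 deaths.

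**3. What r estimates.** If everyone is followed for exactly 18 months with no loss, the variable is min(T, 18), and r is the correlation of BSA change with survival restricted to 18 months. If follow-up runs from the end of therapy, its maximum varies with doses received: 18 months + 28 days = 18.9 months after two doses, 22.6 after six. With that or with early loss, this reading no longer applies.

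**4. Size of the effect when an association exists.** Simulation with n = 20, all alive at 2 months, exponential survival after the landmark given BSA change, calibrated to 43.3% alive at 18 months, hazard ratio 2.0 per SD. The skewed case uses a log ratio with SD 0.6.

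| BSA change | Mean r, true times | Censored at 18 months | Censored at 22.6 months |
|---|---|---|---|
| Normal | -0.49 | -0.42 | -0.45 |
| Skewed | -0.42 | -0.42 | -0.44 |

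The sampling SD of r here is about 0.18. The skewed result is for this hazard ratio and this shape only. In the normal case, unrelated early loss of 10% or 20% by 18 months moves the 18-month value to -0.40 or -0.37.

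**5. No true association.** If censoring is unrelated to BSA change, mean r is 0 and a two-sided 5% test of r keeps about 5% size. If 10% or 20% of patients are lost early, all from the half with worse BSA change, mean r is about -0.07 or between -0.13 and -0.15. A harsher assumption, the worst 10% to 15% lost at months 2 to 6, gives -0.22 to -0.30.

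**6. What each planned analysis uses.**

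| Analysis | BSA change | Survival |
|---|---|---|
| Pearson r | continuous | time, censoring ignored |
| t-test | continuous | status at 18 months |
| Kappa | binary | status at 18 months |
| Landmark Cox | binary | time, censoring handled |

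No row combines continuous change with a method for censored times.

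**The case against.** The plan attaches no test, threshold or decision to r. It is one descriptive number beside a scatter plot in an exploratory study, and the same paragraph plans landmark Kaplan-Meier and Cox analyses. The attenuation of 0.04 to 0.07 in the normal case is small against a sampling SD of 0.18. As a guide only, since no test of r is planned, replacing Pearson with a permutation test from a continuous Cox model gains 0 to 3 points of power with normal change (8 to 9 with the assumed skew). The hazard ratio would rest on only about 11 to 13 deaths. All of this stands and keeps the point minor.

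The censored shares can also be questioned, because a patient needs a month-2 scan to enter the correlation. Given survival to month 2, the same exponential gives exp(-ln 2 × 16/14.9) = 47.5% and exp(-ln 2 × 20.6/14.9) = 38.4%. That raises the share slightly. The plan itself applies 43% to its 20 evaluable patients, and the conclusion does not change.

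Three stronger readings are tempting, and the documents do not support them:

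- **That continuous BSA change is never analysed in a way that copes with censoring.** The t-test uses it against 18-month status. When that status is known for everyone, later censoring cannot affect the test. It is also the comparison that the objectives in Section 2 ask for.
- **That r will produce false positives.** This needs follow-up to depend on BSA change, and the documents give no loss rate or pattern from which to predict that.
- **That the differing follow-up lengths make this defect more serious.** They change the censored share from 43% to 35%, but they are a separate inconsistency.

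**Conclusion.** The point holds, as minor. The stated method enters censored follow-up as time to death for roughly 35% to 43% of patients on the plan's own survival assumption, and no planned time-to-event model uses continuous BSA change. The practical harm is small: modest attenuation if BSA change is normal, none at a hazard ratio of 2.0 under the skewed shape examined, and bias under no association only if follow-up is related to BSA change. The primary endpoint, sample size, decision rule and t-test are unaffected. The censored shares rest on the plan's exponential. The values of r rest on an assumed hazard ratio, assumed distributions and assumed loss patterns.

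**What to change.** In Section 8, Secondary Aims:

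- Add to the existing 2-month landmark analysis a Cox model with percent change in BSA from baseline to T3 as a continuous covariate. Report the hazard ratio, for example per 30-percentage-point decrease, with its 95% CI as the measure of association with survival time. State that it rests on about 11 to 13 expected deaths and will be imprecise. In simulation with normal change and n = 20, the Wald interval covered 94.7% to 96.2%.
- If Pearson r is still shown, label it descriptive, and mark censored patients on the scatter plot.
- Use the same approach for the exploratory biomarkers measured by the landmark.
- Keep the 18-month t-test and the response-based Kaplan-Meier and Cox analyses.

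The cost is SAP wording and slightly more analysis work, with no new data. As a separate point, reconcile the follow-up length in the Section 8 Timeline with Sections 5.2.3 and 7.1.1.
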